After 180 minutes posttreatment, subjects will resume insulin pump therapy, if applicable, and will be given a meal. Subject may be discharged after 180 minutes posttreatment if their plasma glucose is > 100 mg/dL (5.56 mmol/L) and if medically stable. At the Investigator’s discretion, subjects’ prescribed insulin regimen can be restarted, or the meal can be given sooner, but not earlier than 90 minutes post-glucagon treatment, to prevent hyperglycemia or rebound hypoglycemia.

After a wash-out period of 7 to 28 days, subjects will return to the CRC and the study procedures will be repeated with each subject crossed over to the other treatment. After study-related procedures are performed on each of the treatment days, subjects will be discharged. A Follow-Up Visit will be

XSGP-304 Clinical Protocol
G-Pen (glucagon injection)

	
conducted 2 to 7 days after administration of the final dose of study drug as a safety check.
 
Tolerability will be assessed by comparing AE reports between the G-Pen and GlucaGen Hypokit treatment groups. In addition, at the end of each treatment period the subjects will complete questionnaires to assess injection site discomfort, and the Investigator will use a modified Draize scale to evaluate the injection sites after each administration.

Data management and statistical analysis:	
Data will be entered into an electronic Case Report Form (eCRF) by the study site personnel. Data will be monitored at on-site visits by Xeris personnel or by a contract research organization (CRO) delegated by Xeris. A stand-alone Statistical Analysis Plan (SAP) will be written to detail all protocol specified analyses. The SAP will take precedence over the protocol. The primary endpoint will be analyzed using an exact test procedure based on the conditional distribution for a maximum clinically acceptable non-inferior margin of $\leq 5\%$.

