5. Subcutaneous administration of the study drug will be made to the abdomen around the umbilicus as per [Section 9.3.3](#). Clock time of study drug administration will be recorded in the source documents. After study drug injection, the study product will be disposed in a location away from the subject in a manner that maintains the blind. After disposal, the blindfold and headphones will be removed from the subject.
6. Following study drug administration, plasma glucose will be measured every 5 ± 2 minutes through 90 minutes, and every 30 ± 2 minutes thereafter through 180 minutes post-dosing.

7. At 180 minutes post-dosing, the subject will resume insulin therapy and be given a meal as per the standard practice at each site. The subject can be discharged from the clinic if their plasma glucose is >100 mg/dL (> 5.55 mmol/L) and the subject is deemed medically stable.
8. After study drug administration and before 180 minutes post-dosing, if rising glucose levels are observed and if deemed medically necessary, insulin therapy or other medical intervention may be initiated by the Investigator.
 - a. Such intervention is not recommended to occur before 90 minutes post-dosing of study drug.
 - b. Plasma glucose data and assessments of neuroglycopenic symptoms will be censored after the time of intervention, per the statistical analysis plan.
 - c. These interventions (such as insulin, carbohydrates, or a meal) prior to 180 minutes post study drug administration should be captured in the source documents, and further glucose measurements may be performed at the discretion of the Investigator.

Hypoglycemia Symptom Assessments

Subjects will complete a questionnaire regarding severity of hypoglycemia symptoms ([Appendix 1](#)) at the following time points:

1. Just before the IV bolus push dose of insulin is given at the start of the hypoglycemia induction procedure (baseline),
2. Every time blood is drawn for evaluation of plasma glucose concentration during the induction procedure,
3. Just before study drug is administered,
4. Every 5 ± 2 minutes after glucagon is administered until 90 minutes post-dosing, and every 30 minutes (coinciding with plasma glucose measurements) between 90 and 180 minutes post study drug administration.

Local Tolerability and Adverse Events

Local tolerability and AEs will be assessed as follows:

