13.3. Primary Endpoint

The primary endpoint comparison will be performed using both the Intention to Treat (ITT) and the per-protocol (PP) populations. The evaluable set for the PP population will be defined as all randomized subjects who, during both study periods, successfully complete the insulin induction procedure, fulfill the criteria for having achieved a hypoglycemic steady state, and successfully receive a dose of both study drugs (G-Pen followed by GlucaGen Hypokit, or GlucaGen Hypokit followed by G-Pen). For analysis of the primary endpoint, a failure for the study treatment (G Pen or GlucaGen Hypokit) will be recorded if the increase in plasma glucose remains < 20 mg/dL (< 1.11 mmol/L) throughout the 0- to 30-minute period from injection of study drug, while a success is defined as an increase in plasma glucose ≥ 20 mg/dL (≥ 1.11 mmol/L) in subjects from a state of insulin-induced hypoglycemia within the 0- to 30-minute period from injection of study drug.

Non-inferiority will be established based on the calculated 95% confidence interval for the difference in failure rates between G-Pen and GlucaGen Hypokit. Non-inferiority will be declared if the upper limit of the 95% confidence interval for the difference in failure rates is $\leq 5\%$; where the absolute failure rate of G-Pen treatment is $\leq 5\%$.

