2 INTRODUCTION

This documentation describes the planned data analyses for clinical trial XSGP-304 sponsored by Xeris Pharmaceuticals, Inc.

This SAP supersedes the statistical considerations identified in the protocol; where considerations are substantially different these differences will be identified. If additional analyses are required to supplement objectives described in the SAP, they may be performed and will be identified in the Clinical Study Report (CSR).

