5.1.3 Per-Protocol Population (PP)

The Per-Protocol (PP) population is defined as all randomized patients who during both study periods successfully receive a dose of both study drugs (G-Pen followed by GlucaGen Hypokit or GlucaGen Hypokit followed by G-Pen) and have no any major protocol deviations. The actual treatment received will be used for analysis.

Primary endpoint comparison and secondary efficacy analyses will be performed for ITT, mITT and PP populations.

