5.3.6.2 Secondary Endpoints

5.3.6.2.1 Pharmacodynamic (PD) Parameters

The PD endpoints will be derived from the individual glucose profiles. Pharmacodynamic characteristics, including:

- AUC_{0-90} and AUC_{0-180} : plasma glucose area under the concentration versus time curve for 90 and 180 mins from glucagon administration;
- C_{max} : Maximum concentration of glucose in plasma;
- T_{max} : time (in mins) when Glucose C_{max} is reached;

The following rules will be used for incomplete data:

- AUC: If there are missing data points before the last observed value, they will be extrapolated using the last two data points;
- AUC: If there are missing data points after the last observed value, they will not be imputed, and the AUC will be treated as not defined;
- If insulin starts after receiving glucagon, the glucose values post insulin start will be censored out and considered as missing. This is also considered a major protocol deviation.

Comparison between the treatments will be performed using a mixed model with treatment, period and treatment*period as fixed factors and subject as a random factor.

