6.5 Analysis of Primary Endpoint

The primary endpoint analysis will be based on the risk difference in rates of failing to achieve Positive Plasma Glucose Response (PGR) of G-Pen versus GlucaGen Hypokit and a 95% CI will be calculated. Non-inferiority will be declared if the upper limit of the 95% confidence interval for the difference in failure rates is $\leq 5\%$; where the absolute failure rate of G-Pen treatment is $\leq 5\%$. This analysis will be repeated for ITT, mITT and PP populations.

Subjects who are missing the primary endpoint for a study treatment will be considered as having a failure in the primary analysis for that treatment administration. This imputation will be conducted for both the ITT and the mITT populations. If a subject received the same two treatment administrations for both periods (Period 1 and Period 2), only the visit with the planned treatment received will be included in the primary analysis and the subject will be considered a failure in the primary analysis for the for unreceived treatment administration (ITT, mITT). For all other analyses, data will be included for only the planned treatment received in those analyses.

A sensitivity analysis will be performed for where all missing data will be considered a success and the same analysis as above completed.

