10 DEVIATIONS FROM PLANNED ANALYSIS

For timing parameters mixed model analysis was replaced by time-to-event analysis.

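### The SAP counts protocol-permitted insulin after glucagon as a major deviation, so the per-protocol set loses subjects for an act that, after 30 minutes, cannot change the primary endpoint

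*SAP*

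**What the plan says.** **The label.** SAP 5.3.6.2.1, on pharmacodynamic parameters, states that if insulin starts after glucagon, glucose values from then on "will be censored out and considered as missing. This is also considered a major protocol deviation". The sentence gives no time limit. SAP 5.1.3 requires PP subjects to "have no any major protocol deviations". SAP 6.5 says of the primary comparison: "This analysis will be repeated for ITT, mITT and PP populations".

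**The permission.** Protocol 10.2.1.2 lets the investigator start insulin or another intervention before 180 minutes if glucose is rising and there is medical need. It adds: "Such intervention is not recommended to occur before 90 minutes post-dosing of study drug". The same section has the subject resume insulin at 180 minutes. The synopsis says that subjects' "prescribed insulin regimen can be restarted, or the meal can be given sooner, but not earlier than 90 minutes post-glucagon treatment".

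**The protocol's PP set.** Protocol 13.3 takes randomized subjects who in both periods complete induction, "fulfill the criteria for having achieved a hypoglycemic steady state, and successfully receive a dose of both study drugs". It does not mention major deviations.

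**Disclosure.** SAP section 2 says the SAP supersedes the protocol's statistical text, but that "where considerations are substantially different these differences will be identified". SAP section 10 has one entry: "For timing parameters mixed model analysis was replaced by time-to-event analysis".

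**Censoring point.** SAP 4.1 sets the start of censoring at drug administration and applies it only if insulin restarts before 180 minutes. The protocol text that it reproduces censors from the intervention, and SAP 5.3.6.2.1 censors from the start of insulin.

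**The concern.** A PP exclusion should remove data that a deviation could have distorted. The primary endpoint is settled within 30 minutes of injection, so insulin at, say, 100 minutes comes too late to alter it. Excluding that subject discards two valid paired outcomes because of something the protocol allows.

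PP is one of the two populations that protocol 13.3 names for the non-inferiority comparison. Neither document says which population decides if they disagree. A smaller PP set widens the interval against a fixed 5% margin, and it may also drop failures. Read literally, the label has no 180-minute limit; because subjects resume insulin at 180 minutes, it would empty the PP set.

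There is also a minor drafting fault. Taken literally, censoring from drug administration would discard the whole post-dose profile of any subject whose insulin restarts before 180 minutes.

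**Working it through.** **Inputs from the documents.** 111 evaluable, 122 randomized, 10% drop-out (SAP 4.2); non-inferiority if the upper 95% limit for the difference in failure rates is at most 5% and the G-Pen failure rate is at most 5% (SAP 6.5); risk-difference code (SAP Appendix 2). **Assumed:** the share *s* of visits with insulin before 180 minutes, which the documents do not give.

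**The plan's own figure.** 111 × 1.10 = 122.1, which matches 122. Dividing instead, 111/0.90 = 123.3, or 124. The 111 itself cannot be rechecked because no odds-ratio margin is stated, but this point does not depend on it.

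**Loss from PP.** Insulin in either period removes the subject. If visits are independent, 111 × (1 − s)² remain. If the same subjects are affected in both periods, 111 × (1 − s) remain.

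| s (assumed) | independent | same subjects |
|---|---|---|
| 5% | 100.2 | 105.5 |
| 10% | 89.9 | 99.9 |
| 20% | 71.0 | 88.8 |
| 30% | 54.4 | 77.7 |

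**Upper limit.** With *a* G-Pen and *b* comparator failures among *n* subjects per treatment, the Wald limit is (a − b)/n + 1.96 × √[(a/n)(1 − a/n)/n + (b/n)(1 − b/n)/n]. When b = 0 the paired Wald limit is identical.

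For 2 v 0, both failures retained:
- n = 111: 0.01802 + 1.96 × 0.01263 = 4.28%
- n = 95: 4.99%
- n = 94: 0.02128 + 1.96 × 0.01488 = 5.04%
- n = 90: 5.27%

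The G-Pen failure rate at n = 94 is 2/94 = 2.1%, so only the interval criterion is at issue. Reaching 94 means losing 17 of 111. That needs s = 1 − √(94/111), about 8% of visits if independent, or 17/111 = 15% of subjects if the same subjects are affected.

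Other counts:
- 0 v 0: limit 0 at any n
- 1 v 0: 2.66% at 111; above 5% only from n = 58 down (5.07%)
- 2 v 1: 3.94% at 111; above 5% from n = 87 down (5.01%)
- 3 v 0: 5.72% at 111, so it fails without any loss

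**Direction.** Suppose 17 of 111 are lost regardless of outcome and 2 have G-Pen failures.
- Both kept: (94 × 93)/(111 × 110) = 0.716; limit 5.04%
- One kept: (2 × 94 × 17)/(111 × 110) = 0.262; limit 0.01064 + 1.96 × 0.01058 = 3.14%, below the starting 4.28%
- None kept: (17 × 16)/(111 × 110) = 0.022; limit 0

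Loss need not be random. Insulin is prompted by rising glucose, so those lost may mostly be responders. But insulin in one period also removes a subject who failed on the other drug. The sign cannot be settled from the documents.

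**The case against.** **The SAP may redefine PP.** It may, since it supersedes the protocol. But it undertakes to identify substantial differences, and section 10 does not list this one.

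**Only insulin before 180 minutes can be meant.** SAP 4.1 limits censoring in that way, so a reader who inferred that the authors intend an empty PP set would go too far. The limit is still missing from the sentence that creates the deviation, and the narrower reading still covers permitted insulin.

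**PP looks supportive.** ITT is the default for summaries, and missing outcomes are imputed as failures only in ITT and mITT. This suggests a ranking but does not state one. A reader might infer that the rule threatens the trial's main conclusion. The documents do not support that, because ITT and mITT primary results do not change.

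**PP also serves longer analyses.** This stands. SAP 6.6.4 repeats the time-to-event analyses in PP, and symptoms are followed to 180 minutes, so insulin can fall inside that follow-up. Censoring can handle this, and the fix must treat those analyses separately.

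**Very early insulin could matter.** This also stands. Protocol 10.2.1.2 discourages but does not bar insulin before 90 minutes, so insulin within the 30-minute window could affect the endpoint. The point covers only later insulin.

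**Insulin-only censoring against the protocol's wider list.** A reader might infer two conflicting rules, because the reproduced protocol text also names carbohydrates and a meal. The documents do not support that. The protocol leaves this censoring to the SAP, both operative SAP statements use insulin alone, and SAP 5.3.6.2.1 supplies the start point for glucose. What remains is the wrong start point in SAP 4.1, chiefly for symptom data, and an unexplained link to broader text.

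**Conclusion.** The point holds as an inconsistency in the PP definition. The SAP excludes subjects for insulin that the protocol permits, does not list the change, and gains no validity for the primary endpoint when that insulin starts after 30 minutes.

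The consequence is limited to PP. Its size rests on assumed rates of early insulin and on the Wald interval in the SAP code. The PP conclusion would change only in a narrow set of outcomes, such as 2 v 0 failures with both retained and at least 17 of 111 subjects lost. If failures are among those lost, the limit can fall instead. The case for change is that the rule is wrong as written and cheap to correct before outcomes are known, not that it is likely to reverse the trial. The censoring start point in SAP 4.1 is a minor wording correction.

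**What to change.** 1. In SAP 5.3.6.2.1, limit the rule to insulin started before 180 minutes. State that protocol-permitted insulin started after the 30-minute endpoint window is not a major deviation for PP membership in the primary and other 30-minute binary analyses.
2. For PP time-to-event analyses followed to 180 minutes, keep the subject and apply the planned censoring at insulin start. The lifetest code in SAP Appendix 2 has no event/censor indicator and needs one. The planned censoring names glucose and neuroglycopenic symptoms, so say whether autonomic, total and overall-feeling outcomes follow it.
3. List any remaining PP difference from protocol 13.3 in SAP section 10.
4. Reconcile the synopsis, which rules out restart before 90 minutes, with protocol 10.2.1.2, which only advises against it, before setting the status of earlier insulin. No clinical rule is proposed here.
5. In SAP 4.1, start censoring at the intervention that triggers it, and state whether the insulin-only trigger is an intended narrowing of the protocol text reproduced there.

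The cost is SAP wording and a small change to the PP flag and time-to-event code.

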5.3.6.2.2 Hypoglycemia Symptom Mean Scores

Symptoms of hypoglycemia are captured using the following questionnaire:

Neuroglycopenic Symptoms	Severity Score (1-6)
Dizziness	
Blurred vision	
Difficulty in thinking	
Faintness	
Autonomic Symptoms	Severity Score (1-6)
Sweating	
Tremor	
Palpitations	
Feeling of nervousness	
Overall Assessment of Hypoglycemia	Yes/No
Do you currently feel hypoglycemic?	

The following three mean scores will be calculated for each subject at each of the measurement time points:

1. Average Neuroglycopenic Symptom Score (ANS) :

$$\frac{\text{Dizziness} + \text{Blurred vision} + \text{Difficulty in thinking} + \text{Faintness}}{4}$$

4

2. Average Autonomic Symptom Score (AAS):

$$\frac{\text{Sweating} + \text{Tremor} + \text{Palpitations} + \text{Feeling of nervousness}}{4}$$

4

3. Average Total Symptom Score (ATS):

$$\frac{\text{Sum of all symptoms}}{8}$$

8

Overall Assessment of Hypoglycemia:

- this will be treated as a categorical variable and analyzed with descriptive statistics by timepoints;
- additional descriptive summary will be done for overall assessment of hypoglycemia as number and percentage of subjects who: answered “Yes” at baseline, answered “Yes” at baseline and never answered “No” post-baseline, answered “No” at baseline,

answered “No” at baseline and at least once answered “Yes” post-baseline.

This parameter will be analyzed from a decision to dose.

5.3.6.2.3 Time-to-Event Efficacy Endpoints

Symptom relief will be analyzed as aggregate scores for the four autonomic symptoms, four neuroglycopenic symptoms, and 8 total (autonomic and neuroglycopenic) symptoms.

Symptom relief of hypoglycemia is defined as a return to a score (ANS, AAS, and ATS) no more than one unit above euglycemic baseline (1 / 2). Only subjects with baseline score at least 2 or more (for ANS, AAS, or ATS) will be evaluable for this analysis.

Complete resolution of hypoglycemia symptoms is defined as all symptoms in the domain (ANS, AAS, or ATS) have a score of 1 after receiving glucagon.

The time to resolution of the overall feeling of hypoglycemia is defined as first reporting of “No” for the global hypoglycemia question. This will be calculated as the difference (in mins) between the actual time when the first “No” for “Overall Assessment of Hypoglycemia” is observed and the time to decision of glucagon dosing.

Glucagon Preparation Time is defined as time to administer study drug from a decision to dose.

The following timing parameters will be calculated for analysis:

1. Time to a Positive Plasma Glucose Response (PGR) from injection of study drug.
2. Glucagon Preparation Time.
3. Time to symptom relief of autonomic and neuroglycopenic symptoms of hypoglycemia from a decision to dose. That include:
 - time to symptom relief of neuroglycopenic symptoms (ANS) from a decision to dose;
 - time to symptom relief of autonomic symptoms (AAS) from a decision to dose;
 - time to symptom relief of autonomic and neuroglycopenic symptoms (ATS) from a decision to dose;
4. Time to complete resolution of autonomic and neuroglycopenic symptoms of hypoglycemia from a decision to dose. That include:
 - time to complete resolution of neuroglycopenic symptoms (ANS) from a decision to dose;
 - time to complete resolution of autonomic symptoms (AAS) from a decision to dose;
 - time to complete resolution of autonomic and neuroglycopenic symptoms (ATS) from a decision to dose;
5. Time to minimal score of autonomic and neuroglycopenic symptoms of hypoglycemia from a decision to dose. That includes:
 - time to minimal score of neuroglycopenic symptoms (ANS) from a decision to dose;

- time to minimal score of autonomic symptoms (AAS) from a decision to dose;
 - time to minimal score of autonomic and neuroglycopenic symptoms (ATS) from a decision to dose;
6. Time to resolution of the overall feeling of hypoglycemia from a decision to dose. The following rules will be applied:
- only subjects who answered “Yes” at baseline will be evaluable for this analysis;
 - in very rare cases, if subject answers “Yes” all the way to the last time point, the total time to the last assessment will be recorded.

Actual Time will be used for calculations.

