13.4.2. Hypoglycemia Symptoms

Symptom relief will be analyzed as aggregate scores for the four autonomic symptoms, four neuroglycopenic symptoms, and 8 total (autonomic and neuroglycopenic) symptoms (see [Appendix 1](#)).

For analysis, “relief” will be defined as a return to a score no more than one unit above baseline symptoms during the euglycemic baseline period.

The time to the minimal score post baseline will be described and compared between the treatment groups using a mixed model with treatment, period and sequence as terms. Similarly, the time to first reporting of “no” for the overall hypoglycemia question (“Do you currently feel hypoglycemic?”) will be described and compared between the groups.

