APPENDIX 1. HYPOGLYCEMIA SYMPTOM QUESTIONNAIRE

Investigative Site Instructions: The subject should complete the Hypoglycemia Symptom Questionnaire at the following time points:

- Just before the IV bolus push dose of insulin is given at the start of the hypoglycemia induction procedure.
- Every time blood is drawn for evaluation of plasma glucose concentration during the induction procedure.
- Just before study drug is administered.
- Every 5±2 minutes after glucagon is administered until 90 minutes post-dosing. (Data will be collected 18 times).
- Every 30±5 minutes (coinciding with plasma glucose measurements) between 90 and 180 minutes post study drug dosing (90 minutes, 120 minutes, and 180 minutes).

Note: If a subject is unable to physically complete the questionnaire, the subject will provide verbal responses, which will be recorded on the questionnaire by study staff. Documentation will be provided on each completed questionnaire as to who completed the form.

Subject Instructions: Please rate the current intensity (severity) of each of the following symptoms on a scale of 1-6, with a minimum score of “1” meaning the symptom was absent and a maximum score of “6” meaning the symptom was severe. For the final question, please answer “yes” or “no.”

Neuroglycopenic Symptoms	Severity Score (1-6)
Dizziness	
Blurred vision	
Difficulty in thinking	
Faintness	
Autonomic Symptoms	Severity Score (1-6)
Sweating	
Tremor	
Palpitations	
Feeling of nervousness	
Overall Assessment of Hypoglycemia	Yes/No
Do you currently feel hypoglycemic?	

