RUN-IN 1 and RUN-IN 2 analysis phases will include all interventions before dose injections, thereof:

- EUGLYCEMIC BASELINE 1 / 2.

The Euglycemic Baseline phase will be determined as time interval which starts from last 30 minutes of the baseline euglycemic steady state period, covering at least 3 scheduled consecutive plasma measurements in the target range at 0, 15, and 30 minutes used to confirm euglycemic steady state; and stops just before hypoglycemia induction with IV bolus push dose.

Euglycemic Baseline (1 and 2): to determine for the Hypoglycemia Symptoms Assessment scheduled at the end of this phase just before the IV bolus push dose of insulin, will serve as baseline to determine hypoglycemia symptoms relief and/or resolution within Treatment Period (1 and 2). If more than one assessment is performed in this time interval, then the last assessment of each hypoglycemia symptom or score will be selected for use as the baseline.

- HYPOGLYCEMIA INDUCTION (1 and 2). During the induction procedure the subject will enter a state of hypoglycemia through the administration of regular insulin diluted in normal saline within a controlled and monitored setting.

Hypoglycemic steady state (1 and 2): for Treatment Period (1 and 2) is confirmed if:

- penultimate plasma glucose measurement during hypoglycemia induction is < 54.0 mg/dL (< 2.78 mmol/L);
- last plasma glucose measurement during hypoglycemia induction is ≥ 42 mg/dL (≥ 2.33 mmol/L) and < 54 mg/dL (< 2.78 mmol/L); and
- 8-minute linearly extrapolated value from two last measurements of plasma glucose is ≥ 42 mg/dL (≥ 2.33 mmol/L).

Hypoglycemic Baseline (1 and 2). If the subject achieved hypoglycemic steady state then from the last of the last two plasma glucose readings during hypoglycemia induction to time of study drug administration will be defined as Hypoglycemic Baseline for the corresponding treatment period and will serve as baseline for the Primary Endpoint and Secondary Endpoints related to pharmacokinetic and pharmacodynamic characteristics within Treatment Period (1 and 2).

Assessments and Adverse Events with onset in TREATMENT PERIOD 1 or TREATMENT PERIOD 2 will be attributed to the actual treatment and analyzed respectively. Adverse

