6.2 Euglycemic Baseline

Prior to starting the hypoglycemia induction procedure, the subject must have stable plasma glucose for at least 30 minutes at 95 ± 20 mg/dL (75 to 115 mg/dL [4.17 to 6.38 mmol/L]) at a stable IV insulin infusion rate varying no more than $\pm 20\%$ during which plasma glucose must be measured at least every 15 ± 2 minutes (i.e., at least 3 consecutive values in the target range at 0, 15, and 30 minutes).

For Hypoglycemia Symptoms Assessment scheduled at the end of the Euglycemic Baseline phase just before the IV bolus push dose of insulin, will serve as baseline to determine hypoglycemia symptoms relief and/or resolution. If more than one assessment performed in this time interval, then the last assessment of each hypoglycemia symptom or score will be selected for baseline.

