6.3 Hypoglycemic Baseline

Hypoglycemic steady state is defined as a confirmatory plasma glucose value ≥ 42 mg/dL (≥ 2.33 mmol/L) and < 54 mg/dL (< 3 mmol/L), and an 8-minute linearly extrapolated future plasma glucose value ≥ 42 mg/dL (≥ 2.33 mmol/L).

To determine whether a hypoglycemic steady state has been achieved, confirmatory plasma glucose measurements will be taken as necessary at 5, 10 and 15 minutes after an initial plasma glucose < 54 mg/dL (< 3 mmol/L). Depending on the outcome, the following procedures will be followed.

1. If any of the confirmatory measurements meets the criteria for hypoglycemic steady state, the subject will be eligible to receive study glucagon, and further confirmatory plasma glucose measurement are not required.
2. If the final confirmatory plasma glucose value is < 42 mg/dL (< 2.33 mmol/L), the procedure will be terminated, study glucagon will NOT be administered, and the visit will be rescheduled after a minimum 3-day wait. At the Investigator's discretion, the subject should be treated with IV glucose or oral carbohydrates, it should be verified that the subject achieved a euglycemic state and is medically stable prior to discharge.
3. If any of the confirmatory plasma glucose measurements are > 54 mg/dL (> 3 mmol/L), then the IV insulin infusion will be re-started, and insulin adjustments will be made as per the induction procedure. Once another initial plasma < 54 mg/dL (< 3 mmol/L) is obtained, the sequence of up to 3 confirmatory plasma glucose readings will repeated.

If the subject achieved hypoglycemic steady state their linearly extrapolated plasma glucose value from the last two readings of hypoglycemia induction to time of study drug administration will be defined as Hypoglycemic Baseline for corresponding treatment period and will serve as baseline for the Primary Endpoint and Secondary Endpoints related to pharmacokinetic and pharmacodynamic characteristics within Treatment Period 1 / 2.

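### The evaluability rule for symptom relief (baseline score of at least 2) points to the euglycemic baseline, and on the pre-dose reading its threshold still does not match the definition of relief.

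*SAP*

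**What the plan says.** SAP 5.3.6.2.3 defines the event: "Symptom relief of hypoglycemia is defined as a return to a score (ANS, AAS, and ATS) no more than one unit above euglycemic baseline". The next sentence restricts who is analysed: "Only subjects with baseline score at least 2 or more (for ANS, AAS, or ATS) will be evaluable for this analysis". The first sentence names its baseline; the second does not.

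SAP 6.2 says that the symptom assessment made immediately before the insulin bolus "will serve as baseline to determine hypoglycemia symptoms relief and/or resolution". SAP 5.2 says the same for each treatment period. The other candidate, the Hypoglycemic Baseline of SAP 6.3, is a plasma glucose value that "will serve as baseline for the Primary Endpoint and Secondary Endpoints related to pharmacokinetic and pharmacodynamic characteristics"; it is not assigned to symptoms.

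In Protocol Appendix 1 each item runs from 1 to 6, with a score of 1 "meaning the symptom was absent and a maximum score of" 6 marking it as severe. A questionnaire is also completed "Just before study drug is administered" (Protocol 10.2.1.2, Hypoglycemia Symptom Assessments), but neither document names it as a baseline for relief.

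Protocol 13.4.2 defines relief as a "return to a score no more than one unit above baseline symptoms during the euglycemic baseline period" and sets no minimum score. SAP section 10 lists one deviation, the move from a mixed model to time-to-event analysis for timing parameters. It does not mention the minimum score.

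**The concern.** Time to symptom relief should describe subjects whom induced hypoglycemia has made symptomatic and who then recover. An entry rule tied to the euglycemic score selects on something else: symptoms present at 75 to 115 mg/dL, before any hypoglycemia. Protocol 7.1 expects the symptoms to arise below 54 mg/dL, so the subjects that the endpoint is about could be the ones left out.

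Tying the rule to the pre-dose score removes that problem but leaves a mismatch. Entry is set at a fixed 2, while relief is set relative to the subject's own euglycemic score. Where the two overlap, a subject enters the analysis with relief already met, and the result carries no information about the drug. In a yes/no endpoint such subjects are successes on both treatments and pull the comparison toward no difference.

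Because the text does not settle which baseline applies, two programmers could build different analysis sets from it.

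**Working it through.** The plan states no figure for the number evaluable, so there is nothing to reproduce. The check is score arithmetic plus an illustration over assumed shares.

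**Inputs.** Items scored 1 to 6 with 1 = absent (Protocol Appendix 1). ANS and AAS are means of four items and ATS of eight (SAP 5.3.6.2.2). Relief is a score ≤ e + 1, where e is the euglycemic score. Entry is a baseline score ≥ 2 (both SAP 5.3.6.2.3). 122 subjects are to be randomized (SAP 4.2).

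**What a score of 2 requires.** Symptom-free ANS or AAS = 4/4 = 1.0. A mean of 2 needs an item sum of 2 × 4 = 8, four points above the floor. One item at 4 with the rest absent gives (4 + 3)/4 = 1.75, not evaluable; one item at 5 gives (5 + 3)/4 = 2.0, evaluable. For ATS the sum must be 2 × 8 = 16 against a floor of 8.

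**Example subjects.** Let p be the last score before study drug. Relief is already met before dosing when p ≤ e + 1.

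| e | p | Relief threshold e + 1 | Relief met before dosing | In set if baseline = e | In set if baseline = p | In set if p > e + 1 is required |
|---|---|---|---|---|---|---|
| 1.0 | 4.0 | 2.0 | no | no | yes | yes |
| 1.0 | 2.25 | 2.0 | no | no | yes | yes |
| 1.0 | 2.0 | 2.0 | yes | no | yes | no |
| 1.25 | 2.25 | 2.25 | yes | no | yes | no |
| 1.5 | 2.5 | 2.5 | yes | no | yes | no |
| 2.0 | 3.0 | 3.0 | yes | yes | yes | no |

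- Literal reading (baseline = e): the first subject, symptom-free at euglycemia and clearly symptomatic before dosing, is excluded. The last, symptomatic throughout and already within one unit of euglycemia, is included.
- Pre-dose reading (baseline = p): the overlap runs from p = 2.0 to p = e + 1. It is the single value 2.0 when e = 1.0, 2.0 to 2.25 when e = 1.25, and 2.0 to 2.5 when e = 1.5.
- Requiring p > e + 1 removes every overlap. Since e is at least 1.0, it also forces p above 2.0, so the fixed floor of 2 becomes redundant.

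**Size under the literal reading.** The share of subjects with e ≥ 2 is not in the documents. Assuming 1%, 5%, 10%, 20% or 50% of 122 gives about 1, 6, 12, 24 or 61 evaluable. This shows how widely the answer varies; it is not an estimate.

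**Which endpoints.** The rule follows the relief definition, so it governs endpoint 8(a). SAP 5.3.6.2.4 defines endpoint 3 as ANS relief within 30 minutes without repeating the rule, so its application there is implied. Endpoint 4 is met by a glucose response or a symptomatic response, so only its symptom part is touched. Complete resolution, 8(b), requires every item in the domain to equal 1 and carries no entry threshold.

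**The case against.** The strongest reply is that the pre-dose score was plainly meant. SAP 5.3.6.2.3 writes euglycemic baseline in one sentence and plain baseline in the next. Later in the same section, time to resolution of the overall feeling of hypoglycemia is limited to subjects who answered yes at baseline, which makes sense only for a hypoglycemic state. On that reading the clash for a subject with e = 1.0 is one score value, and every higher score works as intended. This stands as evidence of intent. It does not settle the text, because the only symptom baseline that the SAP defines is euglycemic, and the mismatch remains wherever e exceeds 1.0.

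A reader might infer three stronger things that the documents do not support:

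- That almost nobody would be evaluable. The literal reading makes low numbers plausible, but no symptom scores are given.
- That endpoints 4 and 8 fail as a whole. Any glucose responder is a success in endpoint 4 whatever the symptom score, and 8(b) has its own definition.
- That non-evaluable subjects become failures in endpoint 3. If they did, 7 of 122 (5.7%, against 6/122 = 4.9%) would by themselves break the 5% limit on the G-Pen failure rate. But SAP 6.5 writes missing-as-failure for the primary endpoint in the primary analysis, 6.6.1 carries over the test, and 7.1 rules out imputation not otherwise specified. A subject outside an evaluable set is also not the same as a subject with missing data. What can be said is that their handling is unstated.

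**Conclusion.** The concern holds for endpoint 8(a), and by implication for endpoint 3 and the symptom part of endpoint 4. Followed as written, the rule selects on symptoms before induction. On the more likely intended reading, it admits subject-periods in which relief is met before dosing. These results follow from the score definitions and need no assumption about data. How many subjects are affected depends on an unknown score distribution: under the assumed shares above, the literal set ranges from about 1 to 61 of 122. The overlap on the pre-dose reading could be small if most subjects score 1.0 at euglycemia.

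The minimum score is also an addition to the protocol's definition that the SAP does not list as a change. The primary endpoint is untouched, so this is a should-fix item on secondary endpoints.

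**What to change.** In SAP 5.3.6.2.3, replace the restriction with a rule that names its baseline: a subject-period is evaluable for relief in a domain if the score on the last questionnaire before study drug is more than one unit above the same period's euglycemic baseline. Then:

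- State in 5.3.6.2.4 and 6.6.1 that the same set applies to endpoint 3 and that non-evaluable subject-periods are excluded, not counted as failures.
- State that endpoint 4 rests on the glucose response alone in such periods.
- Report the number evaluable by treatment for each domain.
- List the restriction in SAP section 10 as a difference from the protocol.

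The cost is SAP wording and programming; the pre-dose questionnaire is already collected. The downside is that some subjects will be evaluable in only one period. The sample code in SAP Appendix 2 does not pair periods, so as written those subjects can still contribute the period that they have.
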